## **5.6 Study Drug Discontinuation**

Subjects should be discontinued from study drug treatment in the following situations:

- A female subject becomes pregnant
- The subject decides to discontinue study drug treatment, or withdraw consent from the study
- The subject receives a strong CYP3A4 inhibitor
- The subject receives an excluded medication for treatment of pruritus or psoriasis
- Any medical condition that may jeopardize the subject's safety if study drug is continued, in the investigator's and/or Sponsor's opinion
- Discontinuation is deemed to be in the best interest of the subject, in the investigator's and/or Sponsor's opinion
- The subject experiences a NCI CTCAE Grade 3 or higher treatment emergent AE that is assessed as likely related to study drug

The Sponsor or designee should be contacted within 24 hours of investigator's awareness of any study drug treatment discontinuation. Investigators should make every effort to contact the Sponsor or designee before discontinuing study drug treatment, if possible.

Subjects who discontinue treatment with study drug prior to completing the treatment period will have a Follow-up visit 14 days after their last dose of study drug (see [Section 6.5.9](#)). Every effort should be made for subjects to complete the Follow-up visit after a subject has discontinued from study drug.

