## **5.7 Concomitant and Excluded Therapies**

Concomitant therapies include any therapies (including over-the-counter medications) used by a subject from initiation of study drug treatment through the follow-up period. Medications/therapies for which discontinuation was required for the purposes of study participation (i.e., "washout medications/therapies") shall also be documented. A record of all medications used will be maintained for each subject throughout the study. Reported information will include a description of the type of drug, treatment period, dosing regimen, the route of administration, and drug indication.

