### **5.7.2 Excluded Therapies and Study Restrictions**

Therapy exclusions prior to the initial Screening visit are described in [Section 4.3](#). The following therapies and activities are excluded from the initial Screening visit through the follow-up period:

- NK1-R antagonists (other than study drug)
- Systemic biologic therapies, including but not limited to etanercept, infliximab, adalimumab, ustekinumab, secukinumab, or ixekizumab

- Systemic non-biologic psoriasis therapies, including but not limited to systemic corticosteroids, phosphodiesterase-4 inhibitors, Janus kinase inhibitors, cyclosporine, methotrexate, retinoids, hydroxyurea, mycophenolate mofetil, thioguanine, sirolimus, azathioprine, or fumaric acid derivatives
- Topical/local psoriasis therapies other than those permitted per [Section 5.7.1](#), including but not limited to topical corticosteroids, vitamin D analogues, calcineurin inhibitors, phosphodiesterase-4 inhibitors, Janus kinase inhibitors, non-shampoo forms of coal tar, salicylates, retinoids, anthralin, or excimer laser
- Phototherapy, with or without psoralen
- Use of an indoor tanning facility or excessive sun exposure/sunburn
- Systemic therapies with recognized anti-pruritic properties, including but not limited to H1 antihistamines, doxepin, mirtazapine, gabapentin, pregabalin, cannabinoids, and kappa opioid receptor agonists
- Topical anti-pruritic therapies, including but not limited to H1 antihistamines, doxepin, capsaicin, or medicated emollients (e.g., menthol or pramoxine)
- Strong CYP3A4 inhibitors (See [Appendix B](#))
- Any investigational therapy
- Initiation of any bland emollient use after the initial Screening visit

Use of any excluded therapies should be reported to the study medical monitor as soon as possible, and will be recorded as protocol deviations for subjects who receive them.

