## **8.2 Handling of Missing Data and Excluded Therapy Use**

Should a determination of treatment period (on treatment, pre-treatment) be required for adverse events or concomitant medication but the corresponding date is missing, or is a partial date, the event/medication will be considered on treatment unless the portions of the date that are available indicate this is not possible.

The primary method of handling missing efficacy data will be MCMC multiple imputation. Imputation will be conducted within each treatment group independently, so the pattern of missing observations in one treatment group cannot influence missing value estimations in another. For each imputation process, 25 imputations will be performed.

If a subject fails to complete their eDiary for a week or more the primary endpoint (WI-NRS), may be missing. If the Week 8 measure from the eDiary is unavailable because the subject withdrew from the study due to lack of efficacy, or the subject uses an excluded therapy to treat psoriasis or pruritus, their responder status will be defined as non-responder. If the Week 8 value is missing for any other reason, the WI-NRS change from baseline value will be based on imputed data. Missing Week 8 WI-NRS values from which the 4-point responder status is derived will be estimated by MCMC.

Missing WI-NRS data will be derived for the analysis using the method of MCMC multiple imputation. Since both primary and key secondary endpoints require WI-NRS, the following steps will be followed:

1. Using the daily eDiary data, calculate Baseline and Week 2 through Week 8 values by averaging available values. If any values are available, these will be used i.e. a minimum of 1 observation is required to compute a week's average.
2. From step 1, create a dataset for each treatment group, of subjects with observed values and those needing estimation by MCMC. The missing WI-NRS values in each dataset will be filled in using the MCMC method to generate 25 datasets.

The resulting datasets for each treatment arm will be combined into one complete dataset.

Syntax:

```
proc mi data=datain out=dataout seed=&seed. Nimpute=25 <options>;  
  where trtpn=(TRT); /* Note TRT = [1, 2]; depending on treatment group */;  
  mcmc chain=single;  
  var baseline d2 d3 d4 d5 d6 d7 week2 week3 week4 week5 week6 week7 week8;  
run;
```

3. From each complete dataset, the dichotomous responder rate will be determined.

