#### **8.6 Concomitant Medications**

Concomitant medications will be coded by the World Health Organization Drug Dictionary to Anatomical Therapeutic Classification (ATC) and preferred drug name. Concomitant medications will be summarized by ATC level and preferred drug name and listed.

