#### **8.8 Efficacy Analyses**

The efficacy endpoints will be summarized within the FAS and PP populations using descriptive statistics by time point and treatment. Results including averaged imputed values will be summarized at Baseline, Week 2, 4, 8 and Follow-up and the change from baseline for these measures will be summarized at Week 2, 4, 8 and Follow-up. The WI-NRS

measures will also be summarized at Week 6. The WI-NRS and change from baseline will also be presented for each study day. The PGIC is a measure of change and so will only be summarized at Week 2, 4, 8 and Follow-up.

For the 4 and 3 point responder rate endpoints, subjects will be considered responders if they have at least a 4 / 3 point reduction between baseline and the corresponding week and the subject did not use an excluded medication to treat their pruritus or psoriasis.

The difference in the primary efficacy outcome measure (WI-NRS 4-point responder rate at Week 8) will be tested using a CMH test controlling for the ‘as randomized’ stratification factors. Conceptually the hypotheses being tested are:

$$H_0: P_{Placebo} \geq P_{Serlopitant} \quad H_a: P_{Placebo} < P_{Serlopitant}$$

where  $P_{Placebo}$  is the percent of placebo responders and  $P_{Serlopitant}$  is the similar percent for serlopitant. The primary endpoint will utilize the missing data rules as outlined in [Section 8.2](#).

The remaining key secondary endpoints will be analyzed using an analysis of covariance (ANCOVA) model with treatment group and stratification factor as fixed effects and the respective baseline values as a covariate. Both least squares means and observed means will be presented.

To confirm the assumptions for the ANCOVA model (i.e., that the errors are normally distributed with equal variances), residuals will be examined using the Shapiro-Wilk test. If there is overwhelmingly strong evidence that the assumptions are not satisfied, the data will be rank-transformed prior to submitting to the ANCOVA. Results of the rank-transformed analysis then will be considered the primary analysis; however, results of the non-rank-transformed analysis will also be presented.

The preceding analyses are to be conducted for the FAS and PP populations.

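### Do Sections 8.2 and 8.8 give opposite primary-endpoint status to a subject who uses a non-drug excluded treatment?

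*Protocol*

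**What the plan says.** Two places in the protocol tie responder status to excluded treatment.

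- Section 8.2 first deals with a Week 8 diary score that is unavailable after withdrawal for lack of efficacy. The sentence continues: "or the subject uses an excluded therapy to treat psoriasis or pruritus, their responder status will be defined as non-responder".
- Section 8.8 defines a responder, for both the 4-point and the 3-point rates, by the size of the reduction and by the condition that "the subject did not use an excluded medication to treat their pruritus or psoriasis". For the primary endpoint it then refers back to the missing-data rules of Section 8.2.

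The exclusions themselves are in Section 5.7.2, whose title covers excluded therapies and study restrictions. The list includes entries that are not drugs in ordinary language: excimer laser, "Phototherapy, with or without psoralen", and, as its last entry, "Initiation of any bland emollient use after the initial Screening visit". Section 5.6 lists as a reason to stop study drug: "The subject receives an excluded medication for treatment of pruritus or psoriasis".

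**The concern.** Read literally, the two triggers differ in scope. Phototherapy without psoralen is a therapy but hardly a medication. A newly started bland emollient is listed apart from medicated emollients. Section 5.7 writes "Medications/therapies for which discontinuation was required for the purposes of study participation", as if the two words covered different things, and Section 8.6 treats medications as items with a drug name: "Concomitant medications will be coded by the World Health Organization Drug Dictionary to Anatomical Therapeutic Classification (ATC) and preferred drug name".

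Take a subject who has phototherapy for itch and shows a 4-point reduction at Week 8. Section 8.2 would make that subject a non-responder; Section 8.8 would allow a responder. Since Section 5.6 also uses the narrower word, such a subject might stay on study drug and reach Week 8 with an observed score. At stake is the numerator of the primary endpoint. Section 8.8 applies the same condition to the Week 4 key secondary endpoint and to the 3-point rates.

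**Working it through.** **1. How the protocol uses the two words.**

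- Section 6.5.2 describes the mid-screening call as being for subjects who need a washout from prior *therapies*. Footnote 2 of Table 2 (Appendix A) describes the same call, for the same subjects, as following a washout of *medication*. The four-week washout list is exclusion 7 in Section 4.3, which contains phototherapy and excimer laser. Here *medication* already covers light treatment.
- Section 5.7 defines concomitant therapies and then calls the record of them a record of medications. Section 5.7.1 calls it a record of concomitant therapies.
- Sections 5.6, 8.3 and 8.8 say excluded *medication*. Sections 5.7.2, 7.1.6 and 8.2 say excluded *therapy*. There is only one list, in Section 5.7.2.

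**2. How far the Section 8.2 clause reaches.** The clause sits in a sentence that opens with an unavailable Week 8 score, and the next sentence turns to scores missing for other causes. That suggests the clause is itself about unavailable scores. It can also be read as covering any user of an excluded therapy.

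**3. The readings side by side**, for a subject who used phototherapy without psoralen to treat itch or psoriasis:

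| Meaning of *medication* | Reach of 8.2 | Observed 4-point drop | Score missing |
|---|---|---|---|
| Same as *therapy* | Any score | Non-responder in both | Non-responder in both |
| Same as *therapy* | Unavailable only | Non-responder (8.8) | Non-responder in both |
| Drugs only | Unavailable only | Responder (8.8 alone applies) | Non-responder (8.2); 8.8 alone would leave it to the imputed value |
| Drugs only | Any score | **Conflict** | Non-responder (8.2); 8.8 alone would leave it to the imputed value |

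The contradiction for an observed score appears in one row of four. It needs the narrow meaning of *medication* and the wide reach of Section 8.2 together.

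**4. Size.** Inputs from Section 8.1: 100 per arm, 24% placebo response, 43.5% or 46% serlopitant response, one-sided 5% or 2.5%, unstratified chi-squared test.

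Power = Φ[(d − z·s₀)/s₁], where d is the difference in rates, s₀ the pooled and s₁ the unpooled standard error.

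- 24% v 43.5%, one-sided 5%: (0.195 − 1.645 × 0.06687)/0.06544 = 1.299, power 90.3%.
- 24% v 46%, one-sided 2.5%: (0.22 − 1.960 × 0.06745)/0.06564 = 1.338, power 90.9%.

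The stated 90% is reproduced.

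For observed counts, z = (x₁ − x₀)/100 ÷ √[2p̄(1 − p̄)/100]. With x₀ = 24 (the serlopitant counts are assumed):

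| Serlopitant responders | One-sided p |
|---|---|
| 34 | 0.0596 |
| 35 | 0.0440 |
| 36 | 0.0320 |
| 37 | 0.0229 |
| 44 | 0.0014 |

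One relabelled subject crosses 0.025 between 37 and 36, and 0.05 between 35 and 34. Starting from 44, the whole number next above 43.5, the top category is lost only at 36, that is after 44 − 36 = 8 relabelled serlopitant responders.

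The documents give no rate of non-drug excluded treatment. If k responders per 100 are assumed to change status:

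| Arms affected | k | Power at 5% / 2.5% |
|---|---|---|
| Both equally | 1 | 90.7% / 91.3% |
| Both equally | 3 | 91.5% / 92.1% |
| Serlopitant only | 1 | 87.6% / 88.4% |
| Serlopitant only | 3 | 80.6% / 81.7% |
| Placebo only | 1 | 92.9% / 93.4% |

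**The case for a change.** The strongest argument for a change is that calling the words synonyms does not say which entries count. Bland emollients appear among the psoriasis therapies in inclusion criterion 4 and under allowed therapies in Section 5.7.1, so one newly started for itch could be called an excluded therapy. The pointer in Section 8.8 covers only the missing-data rules and only the primary endpoint, so it does not plainly carry the Section 8.2 wording over to Week 4 or to the 3-point rates. And under the third row of the table, the same phototherapy would count against a subject with a missing score but not against one with an observed score.

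Part of this stands: the protocol does not itemise the set, and a newly started emollient is open to two readings. It can equally be a study restriction, since emollient use begun by Screening is to continue and Section 5.7.2 covers activities as well as therapies. On that reading it triggers neither section.

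The remaining supports are weaker. Section 8.6 is about drug coding, not response. The inference from Section 5.6 assumes the narrow meaning it is meant to show. The p-value illustration removes responders from the serlopitant arm only and would apply equally to any rule that relabels one subject.

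**Conclusion.** The wording differs between Sections 8.2 and 8.8, but the protocol's own usage points to one rule set against one list, and the claimed opposite status needs two disputed readings at once. This is a clerical slip plus a detail that analysts fill in. Which Section 5.7.2 entries count against response is ordinary content of the statistical analysis plan, which Section 8 requires to be final before unblinding. The type and indication of each treatment are already recorded under Section 5.7, so nothing is lost by settling it there. Either reading, fixed before unblinding and applied alike to both arms, gives a sound primary analysis.

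The affected group is small in scope: non-drug items used specifically to treat itch or psoriasis, which leaves out incidental use. Its frequency is unknown, and no direction of bias can be claimed. If use is similar in the two arms (an assumption), the stated power is not reduced; a loss arises only if relabelling falls mainly on serlopitant responders. No change to the plan follows.

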## **5.8 Assignment to Treatment**

### **5.8.1 Randomization**

Eligible subjects will be randomized to receive serlopitant 5 mg or placebo in a 1:1 ratio. Stratified permuted block randomization will be used. Randomization will be stratified by the subject's reported WI-NRS score for the 24-hour period prior to the initial Screening visit (7-8, 9-10). An IWRS will be used to perform the randomization.

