### 6.5.1 Screening Visit/Period

Subjects who require a washout from prior therapies per study criteria will have their Screening period start 4 weeks prior to the Baseline visit. Subjects who do not require a

washout from prior therapies will have their Screening period start 2 weeks prior to the Baseline visit. The following screening procedures are to be performed at the Screening visit.

- Informed consent will occur prior to any protocol-mandated procedures, including the stopping of any excluded therapies
- Demographics
- Medical history (including prior medications)
- Worst-Itch Numeric Rating Scale (paper)
- Inclusion/exclusion criteria review
- Complete physical examination
- Vital signs (including height and weight)
- ECG
- Laboratory
  - Hematology
  - Chemistry
  - Urine pregnancy test for females of childbearing potential (with positive or equivocal results confirmed by a serum pregnancy test)
  - Urinalysis
  - Endocrine
  - Reproductive endocrine labs for females under 55 years of age at consent
- BSA
- sPGA
- After training, dispense eDiary with instructions to complete it every day during the Screening Period
- Dispense actigraphy watches with instructions to wear them every day during the Screening Period.
- Schedule the Baseline visit; A minimum of 14 opportunities to complete the WI-NRS in the eDiary are required prior to assessing eligibility.

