## 8 STATISTICAL METHODS

All statistical processing will be performed using SAS® unless otherwise stated. No interim analyses are planned. Endpoints will be summarized with descriptive statistics by treatment group and visit. For continuous variables, the following information will be presented: n, mean, standard deviation, median, minimum and maximum. For categorical variables counts and percentages will be used.

The primary method of handling missing efficacy data will be the method of Markov Chain Monte Carlo (MCMC) multiple imputation. As one sensitivity analysis, the last observation carried forward method (LOCF) will be used (i.e., the last available on-therapy observation for a subject will be used to estimate subsequent missing data points). As a second sensitivity analysis, a repeated measures model will be used on observed data.

Baseline for measures other than the eDiary and actigraphy daily measures, will be the last recorded value prior to the start of treatment. For daily measures including the WI-NRS, baseline will be the average result measured over the week prior to treatment. Additionally, the daily measures will be summarized at Weeks 2, 4, 6 and 8 by averaging the daily results associated with these weeks.

A statistical analysis plan (SAP), describing all statistical analyses will be provided as a separate document. The SAP will be finalized prior to unblinding of the study treatments.

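### The Week 8 and Week 4 responder tests leave out the eDiary baseline from which response is calculated: a valid analysis, but one that gives up a little power (about 0 to 1.5 points)

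*Protocol*

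**What the plan says.** - **Primary test.** Section 8.8: the Week 8 4-point responder rate "will be tested using a CMH test controlling for the" as-randomized stratification factors. The Synopsis (Statistical Methods) uses the same test for the Week 4 responder rate.
- **Stratifier.** Section 5.8.1 names one factor, the "WI-NRS score for the 24-hour period prior to the initial Screening visit", in two bands, 7-8 and 9-10. Section 6.5.1 shows that it is a paper rating taken at the Screening visit, 2 or 4 weeks before Baseline.
- **Baseline for response.** Section 8: for daily measures such as WI-NRS, "baseline will be the average result measured over the week prior to treatment". Section 8.8 defines response as "at least a 4 / 3 point reduction between baseline and the corresponding week", provided no excluded medication was used for pruritus or psoriasis.
- **Baseline elsewhere.** The Day 7 and Day 3 change endpoints use an ANCOVA with "treatment group and stratification factor as fixed effects and the respective baseline values as a covariate" (Section 8.8). Baseline is also a variable in the imputation model (Section 8.2).
- **Power.** Section 8.1 states 90% power with 100 per group from an unstratified chi-squared test. It expects adjustment to improve on this, but credits only the stratification.

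**The concern.** The stratifier and the eDiary baseline are different measurements: one paper score two or more weeks before randomization, cut in two, against a one-week average of daily entries just before dosing. The stratifier is therefore only a partial stand-in for the baseline that enters the endpoint.

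The threshold is a fixed 4 points, and entry requires a weekly average of at least 6 (Section 4.2). A subject starting at 6 must reach 6 - 4 = 2 or less; one starting at 9.5 need only reach 9.5 - 4 = 5.5. If Week 8 itch follows baseline less than one-for-one, subjects with a higher baseline respond more often, and baseline carries information that the primary test does not use. At stake is some power, from data already collected. The protocol takes this step for the continuous key secondary endpoints and not for the responder endpoints.

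**Working it through.** **1. Reproduce the stated power.** Inputs from Section 8.1: n = 100 per group and a pooled-variance chi-squared test without continuity correction. Power = Φ[(d - z·SE0)/SE1], where SE0 = √(2·p̄(1-p̄)/n) and SE1 = √(p1(1-p1)/n + p2(1-p2)/n).

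- 24% vs 43.5%, one-sided 5%: d = 0.195, p̄ = 0.3375, SE0 = 0.0669, SE1 = 0.0654. (0.195 - 1.645 × 0.0669)/0.0654 = 1.30, so power is 90.3%.
- 24% vs 46%, one-sided 2.5%: d = 0.22, p̄ = 0.35, SE0 = 0.0675, SE1 = 0.0656. (0.22 - 1.960 × 0.0675)/0.0656 = 1.34, so power is 90.9%.

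The stated 90% is correct.

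**2. Analytic range.** Let r be the within-stratum correlation of eDiary baseline with response (an assumption; the protocol gives none). Adjustment multiplies the residual variance by 1 - r², so the same precision needs 200 × (1 - r²) patients.

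| r | Patients needed instead of 200 | Power, one-sided 5% (from 90.3%) | Power, one-sided 2.5% (from 90.9%) |
|---|---|---|---|
| 0.1 | 198 | 90.6% | 91.2% |
| 0.2 | 192 | 91.3% | 92.0% |
| 0.3 | 182 | 92.6% | 93.3% |
| 0.4 | 168 | 94.2% | 95.0% |

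**3. Simulation.** Assumed: eDiary baseline mean 8.1, SD 1.06, truncated to 6-10; stratum-baseline correlation 0.48; residual SD 2.4; stratified 1:1 allocation, 100 per arm. The slope is that of the Week 8 score on baseline. Rates are 24% vs 43.5% at one-sided 5%. Cells show CMH power, then baseline-adjusted logistic power; the Wald column used closely similar assumptions.

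| Slope | Likelihood-ratio (4,000 trials) | Score (4,000) | Wald (8,000) | Gain in a further run (6,000) |
|---|---|---|---|---|
| 0.1 | 90.1, 92.1 | 90.1, 92.0 | 90.5, 91.6 | about 1.5 |
| 0.4 | 90.1, 91.2 | 90.2, 91.1 | 90.6, 90.9 | about 0.5 |
| 0.7 | not run | 90.3, 91.0 | 90.2, 90.4 | about 0.3 |
| 1.0 | 91.5, 91.5 | 90.5, 90.6 | 90.5, 90.4 | none |

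At 24% vs 46%, one-sided 2.5%, slope 0.4, the pairs are 91.4 and 92.5 (likelihood-ratio), 91.2 and 92.4 (score), and 91.0 and 91.6 (Wald).

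The Monte Carlo standard error of one power figure from 6,000 trials is √(0.9 × 0.1/6000) = 0.39 points. It is smaller for a difference between two tests run on the same trials, but gains of 0.3 to 0.5 are still close to noise.

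**4. Wider assumptions.** A further set (3,000 trials per setting, SD 2 to 3, stratum-baseline correlation 0.31, score test, both alpha levels) gave 0.1 to 1.3 points at Week 8 slopes of 0.5 and 0.75. It gave 1.3 to 3.5 points at slope 0, where Week 8 itch is unrelated to baseline. At slope 1.0 it showed 0.4 points although baseline then carries no information, so a few tenths of a point in these comparisons are test size or noise.

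**5. Type I error.** In 8,000 null trials in each of three settings, the adjusted score test rejected 5.0 to 5.6% at nominal 5% and 2.3 to 2.6% at nominal 2.5%. The CMH rejected 4.9 to 5.3% and 2.2 to 2.4%.

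**The case against.** The case for leaving the plan alone is strong. A CMH test controlling for the as-randomized factor is valid, matches the randomization and needs no outcome model. The gain is small and rests on a slope, residual SD and correlation that the protocol does not supply. Likelihood-ratio and score figures flatter the adjusted analysis slightly because those tests reject a little more often under the null; with a Wald test the gain at slope 0.4 is 0.3 points at one-sided 5%. A logistic coefficient is also a conditional log odds ratio, whereas Section 8.8 states its hypotheses as responder percentages, so a coefficient test paired with a standardised difference would mix two targets. All of this stands, and it shapes the fix.

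Two stronger readings are tempting. A reader might infer that baseline must be prognostic because the threshold is fixed. It need not be: if the Week 8 score rises one-for-one with baseline, change does not depend on baseline and nothing is gained. A reader might also infer that chance imbalance in the eDiary baseline undermines the comparison. Individual trials can be affected: at slope 0.4, among the roughly 15% of simulated trials with imbalance more than one SD against serlopitant, CMH power was 83.3%, against 89.2% adjusted. But the overall error rate of the CMH already allows for such imbalance and stayed close to nominal.

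What the objection does not remove is that the protocol itself fixes the primary test, so this is not a detail left to the SAP. Section 8.8 also gives no reason for using the baseline for two key secondary endpoints and not for the responder endpoints.

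**Conclusion.** The point holds as a modest efficiency improvement. The Week 8 and Week 4 responder tests adjust only for a two-level paper screening score and omit the continuous eDiary baseline from which response is calculated. Adding it raises power by about 0 to 1.5 points from about 90% for assumed Week 8 slopes of 1.0 down to 0.1. In step 2, a gain of 1.0 point at one-sided 5% (r = 0.2) is worth 200 - 192 = 8 patients. Larger gains need Week 8 itch to be almost or entirely unrelated to baseline. Adjustment cost no power beyond Monte Carlo error in any setting.

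The documents do not support reading this as an invalid primary test or a wrong sample size: the CMH is sound and 90% reproduces. Nor does the protocol disregard the eDiary baseline altogether. It is in the imputation model, though there it affects only missing values and not the test statistic.

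**What to change.** In Section 8.8 and the Synopsis, for the Week 8 and Week 4 4-point responder endpoints:

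1. In each of the 25 imputed datasets, fit a logistic model with treatment, the as-randomized stratum and continuous eDiary baseline WI-NRS. The non-responder rules of Sections 8.2 and 8.8 stay as they are.
2. From the model, average the predicted response probability over all FAS subjects under each treatment and take the difference. This standardised difference is both the estimate and the basis of the one-sided test, so both match the hypothesis on responder percentages in Section 8.8.
3. Pre-specify its variance, delta-method or influence-function, naming one.
4. Combine the differences and variances over the imputations by Rubin's rules.
5. Keep the stratified CMH as a supporting analysis.

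The cost is wording, settled before unblinding, with no new data. Criterion 9a in Section 4.2 requires at least 80% diary completion over the last two weeks: 0.8 × 14 = 11.2, so at least 12 of 14 entries and at least 5 in the baseline week. The downside is small: the primary p-value becomes model-based. If the sponsor prefers to keep the CMH as primary, the adjusted difference can be a pre-specified sensitivity analysis.
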